## 6. STUDY INTERVENTION(S) AND CONCOMITANT THERAPY

### 6.1. Study Intervention(s) Administered

GSK3511294 is a humanised monoclonal antibody (IgG1, kappa) against recombinant human interleukin 5 (IL-5).

GSK3511294 liquid drug product will be supplied by GSK in a CCI [REDACTED]

CCI [REDACTED] The drug product and syringe will be assembled in a single use, disposable safety syringe to enable delivery of the drug product. Each device enables SC delivery of 100 mg GSK3511294 in CCI [REDACTED]

The recommended storage condition is 2 - 8°C, protected from light. The expiry date, where required, is stated on the product label.

An overview of study intervention is provided in [Table 1](#).

**Table 1 Overview of Study Intervention**

ARM Name	GSK3511294
Intervention Name	GSK3511294 Injection
Type	Biologic
Dose Formulation	Sterile liquid formulation in single use PFS
Unit Dose Strength(s)	100 mg/mL, CCI [REDACTED]
Dosage Level(s)	100 or 300 mg (Day 1); 300 mg given as 3 separate injections given in the upper arm and separated by at least 5 cm.
Route of Administration	SC injection
Use	Experimental
IMP and NIMP	IMP
Sourcing	Provided centrally by the Sponsor
Packaging and Labelling	Study Intervention will be provided in PFS. Each PFS will be labelled as required per country requirement.

PFS=Pre-filled safety syringe, IMP=Investigational Medicinal Product

#### 6.1.1. Medical Devices

CCI [REDACTED]

CCI

All device deficiencies, (including malfunction, use error and inadequate labelling) shall be documented and reported by the investigator throughout the clinical investigation (see Section 8.3.6) and appropriately managed by GSK.

## **6.2. Packaging and Labelling**

The contents of the label will be in accordance with all applicable regulatory requirements.

## **6.3. Preparation/Handling/Storage/Accountability**

1. The investigator or designee must confirm appropriate temperature conditions have been maintained during transit for all study intervention received and any discrepancies are reported and resolved before use of the study intervention.
  2. Only participants enrolled in the study may receive study intervention and only authorized site staff may supply or administer study intervention. All study interventions must be stored in a secure, environmentally controlled, and monitored (manual or automated) area in accordance with the labelled storage conditions with access limited to the investigator and authorized site staff.
  3. The investigator, institution, or the head of the medical institution (where applicable) is responsible for study intervention accountability, reconciliation, and record maintenance (i.e., receipt, reconciliation, and final disposition records).
  4. Further guidance and information for the final disposition of unused study intervention are provided in the SRM.
- Under normal conditions of handling and administration, study intervention is not expected to pose significant safety risks to site staff.
  - A Material Safety Data Sheet (MSDS)/equivalent document describing occupational hazards and recommended handling precautions either will be provided to the investigator, where this is required by local laws, or is available upon request from GSK.

#### **6.4. Measures to Minimize Bias: Randomization and Blinding**

Not applicable, as this study is an open-label, single dose study.

#### **6.5. Study Intervention Compliance**

When participants are dosed at the site, they will receive study intervention directly from the investigator or designee, under medical supervision. The date and time of each dose administered in the clinic will be recorded in the source documents. The dose of study intervention and study participant identification will be confirmed at the time of dosing by a member of the study site staff other than the person administering the study intervention.

#### **6.6. Dose Modification**

There are no specific adjustment/stopping criteria for this study. Each participant will receive a single dose of GSK3511294 100mg or 300 mg subcutaneously in this study.

#### **6.7. Continued Access to Study Intervention after the End of the Study**

Participants will not receive any additional treatment from GSK after completion of the study because only healthy participants are eligible for study participation.

#### **6.8. Treatment of Overdose**

The dose of GSK3511294 that is considered to be an overdose has not been defined. There are no known antidotes and there is no specific treatment for a suspected overdose. In FTIH study 205722 (refer to the GSK3511294 Investigator's Brochure (GSK Document Number [2016N295843\\_03](#)), single SC doses of GSK3511294 up to 300 mg were well tolerated by adult participants with mild/moderate asthma (6 participants received a 300 mg SC dose).

Each PFS will enable the delivery of a 100 mg single dose of study intervention (see Section [6.1](#)). In the event of an overdose, the investigator should:

- Contact the Medical Monitor immediately.
- Treat the patient with active supportive care as dictated by the subject's clinical status in the knowledge of the long half-life (approximately 41 days) of GSK3511294.
- Closely monitor the participant for AE/SAE and laboratory abnormalities for 30 weeks following the last administered dose.
- Document the quantity of the excess dose as well as the duration of the overdosing in the CRF.

## 6.9. Concomitant Therapy

Participants must abstain from taking prescription or non-prescription drugs (including vitamins, recreational drugs, and dietary or herbal supplements) within 7 days (or 14 days if the drug is a potential enzyme inducer) or 5 half-lives (whichever is longer) before the start of study intervention until completion of the follow-up visit, unless, in the opinion of the investigator and sponsor, the medication will not interfere with the study procedures or compromise subject safety.

Recreational drug use and QT prolonging medications are not allowed throughout the study.

Paracetamol (acetaminophen)  $\leq 2\text{g/day}$  as a mild analgesic is allowed throughout the study.

Any concomitant medication (eg. Vaccines) may be considered on a case-by-case basis by the investigator in consultation with the Medical Monitor if required. (Note: Any approved COVID-19 vaccine by local government is permitted, but it should avoid to be administered within 14 days of GSK3511294. If the vaccination within 14 days is unavoidable, then alternative time interval can be considered on a case by case basis in conjunction with the medical monitor. Experimental COVID-19 vaccines are not permitted.)

Any medication or vaccine (including over-the-counter or prescription medicines, vitamins, and/or herbal supplements) that the participant is receiving at the time of enrolment or receives during the study must be recorded in the eCRF along with:

- reason for use
- dates of administration including start and end dates
- dosage information including dose and frequency

The Medical Monitor should be contacted if there are any questions regarding concomitant or prior therapy.

## 7. DISCONTINUATION OF STUDY INTERVENTION AND PARTICIPANT DISCONTINUATION/WITHDRAWAL

### 7.1. Discontinuation of Study Intervention

There is no specific discontinuation of study intervention criteria for this study. Each participant will receive a single dose of GSK3511294 100mg or 300 mg subcutaneously in this study.

## **7.2. Participant Discontinuation/Withdrawal from the Study**

- A participant may withdraw from the study at any time at his/her own request or may be withdrawn at any time at the discretion of the investigator for safety, behavioural or compliance reasons. This is expected to be uncommon.
- Participants are strongly encouraged to remain in the study for the entire duration but may prematurely withdraw from the study at any time at his/her own request, at the request of their legally authorized representative (LAR), or may be withdrawn at any time at the discretion of the investigator for safety, behavioural, or compliance reasons. This is expected to be uncommon.
- Participants who prematurely withdraw from the study should attend:
  - a Withdraw from Study (WS) Visit, 26 weeks after the administered dose of study intervention AND
  - a Follow-up visit/call, 30 weeks after the administered dose of study intervention for AE/SAE.
- If the participant withdraws consent for disclosure of future information, the sponsor may retain and continue to use any data collected before such a withdrawal of consent.
- If a participant withdraws from the study, he/she may request destruction of any samples taken and not tested, and the investigator must document this in the site study records.

## **7.3. Lost to Follow Up**

A participant will be considered lost to follow-up if he or she repeatedly fails to return for scheduled visits and is unable to be contacted by the study site.

The following actions must be taken if a participant fails to return to the clinic for a required study visit:

- The site must attempt to contact the participant and reschedule the missed visit as soon as possible and counsel the participant on the importance of maintaining the assigned visit schedule and ascertain whether or not the participant wishes to and/or should continue in the study.
- Before a participant is deemed lost to follow up, the investigator or designee must make every effort to regain contact with the participant (where possible, 3 telephone calls and, if necessary, a certified letter to the participant's last known mailing address or local equivalent methods). These contact attempts should be documented in the participant's medical record.
- Should the participant continue to be unreachable, he/she will be considered to have withdrawn from the study.
- Site personnel, or an independent third party, will attempt to collect the vital status of the participant within legal and ethical boundaries for all participants.

Public sources may be searched for vital status information. If vital status is determined as deceased, this will be documented and the participant will not be considered lost to follow-up. Sponsor personnel will not be involved in any attempts to collect vital status information.

## **7.4. Criteria for increased monitoring of individual participants**

### **7.4.1. Liver chemistry**

**Liver chemistry increased monitoring criteria** and required actions and follow-up assessments have been designed to assure participant safety and evaluate liver event aetiology. Since this is a single dose study liver chemistry stopping criteria do not apply. If the following criteria are met increased liver chemistry monitoring is required:

- ALT  $\geq 3 \times \text{ULN}$
- ALT  $\geq 3 \times \text{ULN}$  AND bilirubin  $\geq 2 \times \text{ULN}$  ( $>35\%$  direct bilirubin) or (International

Normalized Ratio) INR  $>1.5$

See [Appendix 5](#) for guidance regarding increased monitoring of liver chemistry and required actions and follow-up assessments.

### **7.4.2. QTc**

A detailed assessment including a concomitant assessment for PK, renal chemistry and electrolytes (potassium, calcium and magnesium), toxicology screen and clinical evaluation (e.g. continuous cardiac monitoring, admission for direct observation or referral) and discussion with the GSK medical monitor will be triggered in the following scenarios:

#### Refer for hospital admission & cardiology consult

- Arrhythmia or evidence of clinical impact e.g. syncope.

Direct observation for 24 hours before discharge with 48 h ambulatory Holter monitor and subsequent repeat assessment at 48 h\*.

- QTcF change from baseline  $> 60$  msec and no clinical impact. (Baseline is the average of triplicate readings at pre-dose on Day 1).
- QTcF  $> 500$  msec or uncorrected QT  $> 600$  msec and no clinical impact.

\* If QTcF (or QT if  $> 600$  msec) remains the same/increases on assessment at 24 h (end of direct observation) and 72 h periods (after 48 h Holter monitor), then remain the observation and consideration of cardiology consult.

Notes: the QTcF should be based on averaged QTcF values of triplicate electrocardiograms obtained over a brief (up to 10 minutes) recording period.

## **7.5. Criteria for Follow-up of Potential Type III Hypersensitivity (Immune Complex Disease /Vasculitis)**

Owing to the adverse findings of arterial inflammation that were observed in the 1-month, but not at the 6-month, nonclinical toxicology studies, events potentially representing type III hypersensitivity/immune complex disease/vasculitis should be promptly reported to GSK, and consultation with the medical monitor is encouraged. Treatment for the event will be given as medically required. If possible, PK, ADA, C3, and C4 samples may be taken at the time of the event along with haematology, clinical chemistry and urinalysis.

Symptoms potentially suggestive of vasculitis include but are not limited to:

- persistent\* fever (\*where persistent is considered to be a duration of  $\geq 2$  days)
- persistent\* muscle and joint pain
- persistent\* rash
- persistent\* fatigue
- symptoms of peripheral neuropathy, like numbness or weakness
- laboratory abnormalities, e.g., decreased platelets, elevated creatinine, decrease in complement C3/C4, abnormal urinary albumin/creatinine ratio

Participants who experience any of the above events should be monitored until the event resolves and/or a diagnosis is established.

The symptoms and clinical features are often non-specific and heterogenous with respect to the time course over which they develop, organ involvement and the constellation of symptoms and severity. Early recognition of potential events of vasculitis is important to timely diagnosis and subsequent treatment.

The precise management will depend on the clinical evaluation at the time of presentation and ongoing assessment including consideration of relevant differential diagnoses. Given that there is often a differential for presenting symptoms such as infection, and indeed such factors may also precipitate immune related AEs, these factors (infectious, neoplastic, metabolic, toxic) should be given due consideration and ruled out.

Serological, immunological, and histological (biopsy) data should be considered to support the diagnosis and consultation with the GSK medical monitor, and an appropriate medical specialist should be considered when investigating a possible immune related AE.

Unscheduled PK, ADA, C3 and C4 samples may be taken at the time of the event and samples may be taken for additional biomarkers (e.g., ANA, anti-neutrophil cytoplasmic antibodies [ANCA]) in the setting of clinical concern regarding the possibility of immune complex disease. If necessary, testing for biomarkers, e.g., ANA, ANCA (anti-myeloperoxidase [MPO] antibody and anti-proteinase 3 [PR3] antibody), may also be conducted using the frozen baseline serum samples (that were collected and stored prior to administration of study intervention) to allow for

evaluation of interval change for participants with suspected vasculitis (see Section 8.7). Other possible causative or differential factors for abnormal clinical or laboratory observations may also have to be investigated including testing to exclude infection.

If clinically indicated, the participant may be referred to a specialist for further management, which may include organ biopsy.

## **8. STUDY ASSESSMENTS AND PROCEDURES**

- Study procedures and their timing are summarized in the SoA (Section 1.3).
- Protocol waivers or exemptions are not allowed
- Immediate safety concerns should be discussed with the sponsor immediately upon occurrence or awareness.
- Adherence to the study design requirements, including those specified in the SoA, is essential and required for study conduct.
- All screening evaluations must be completed and reviewed to confirm that potential participants meet all eligibility criteria. The investigator will maintain a screening log to record details of all participants screened and to confirm eligibility or record reasons for screening failure, as applicable.
- Procedures conducted as part of the participant's routine clinical management (e.g., blood count) and obtained before signing of ICF may be utilized for screening or baseline purposes provided the procedure met the protocol-specified criteria and was performed within the time frame defined in the SoA (Section 1.3.). Repeat or unscheduled samples may be taken for safety reasons or for technical issues with the samples. The maximum amount of blood collected from each participant over the duration of the study, including any extra assessments that may be required, will not exceed 70 mL.

### **8.1. Efficacy Assessments**

Not applicable. This study is an open-label single dose PK study in healthy Chinese participants. There is no efficacy outcome for this study.

### **8.2. Safety Assessments**

- Planned time points for all safety assessments are provided in the SoA (Section 1.3). Additional time points for safety tests (such as vital signs, physical exams and laboratory safety testes) may be added during the course of the study based on newly available data to ensure appropriated safety monitoring.

**8.2.1. Physical Examinations**

- A complete physical examination will include, at a minimum, assessments of the Skin, Cardiovascular, Respiratory, Gastrointestinal and Neurological systems. Height and weight will also be measured and recorded.
- A brief physical examination will include, at a minimum, assessments of the skin, lungs, cardiovascular system, and abdomen (liver and spleen).
- Investigators should pay special attention to clinical signs related to previous serious illnesses.

**8.2.2. Vital Signs**

- Oral or skin temperature, systolic and diastolic blood pressure, pulse and respiratory rate will be assessed.
- Blood pressure and pulse measurements will be assessed in the resting state with a completely automated device. Manual techniques will be used only if an automated device is not available.
- Blood pressure and pulse measurements should be preceded by at least 5 minutes of rest for the participant in a quiet setting without distractions (e.g., television, cell phones).
- Blood pressure and heart rate will be measured in triplicate before dosing; single measurements after dosing. Single temperature and respiratory rate measurements will be measured at all time points.

### 8.2.3. Electrocardiograms

Triplicate 12-lead ECG will be obtained as outlined in the SoA (see Section 1.3) using an ECG machine that automatically calculates the heart rate and measures PR, QRS, QT, and [QTc] intervals. ECG will be measured in supine position after 5 minutes rest.

### 8.2.4. Clinical Safety Laboratory Assessments

- All protocol required safety laboratory assessments will be conducted in CRU's laboratory. See [Appendix 2](#) for the list of clinical laboratory tests to be performed and to the SoA (Section 1.3) for the timing and frequency. The preparation and shipment of samples will follow CRU guideline. Reference ranges for all safety parameters will be provided to GSK by the laboratory responsible for the assessments.
- The investigator must review the laboratory report, document this review, and record any clinically significant changes occurring during the study as an AE. The laboratory reports must be filed with the source documents.
- All laboratory tests with values considered clinically significantly abnormal during participation in the study should be repeated until the values return to normal or baseline or are no longer considered significantly abnormal by the investigator or medical monitor.
  - If clinically significant values do not return to normal/baseline within a period of time judged reasonable by the investigator, the etiology should be identified and the sponsor notified.
- All protocol-required laboratory tests, as defined in Section 10.2, must be conducted in accordance with the laboratory manual and the SoA (Section 1.3).
- If laboratory values from non-protocol specified laboratory tests performed at the institution's local laboratory require a change in participant management or are considered clinically significant by the investigator (e.g., SAE or AE or dose modification), then the results must be recorded.

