1.1. Objectives, Estimands and Endpoints

Objectives	Endpoints
Primary	

 To evaluate the plasma pharmacokinetics of single subcutaneous doses of GSK3511294 in Chinese healthy participants 	
 Plasma pharmacokinetic parameters of GSK3511294 after a single subcutaneous dose: AUC(0-∞), AUC(0-t), AUC(0-Week4), AUC(0-Week12), AUC(0-Week26), %AUCex, Cmax, tmax, tlast, CL/F, Vz/F, λ_z and $t_{1/2}$ when assessable*
Secondary	

 To assess the safety and tolerability of single subcutaneous (SC) doses of GSK3511294 in Chinese healthy participants 	
 Incidence of adverse events (AE), serious adverse events (SAE) Change from baseline in laboratory safety data, at each post-dose timepoint during the 26 week treatment period, which including hematology and clinical chemistry Absolute values of C3 & C4 at each timepoint and the ratio to baseline at each post-dose timepoint during the 26 week treatment period Change from baseline in vital signs, at each post-dose timepoint during the 26 week treatment period, which including blood pressure, body temperature and pulse rate

Objectives	Endpoints

 To assess the immunogenicity of GSK3511294 in Chinese healthy participants 	
 Change from baseline in Electrocardiograms (ECG), at each post-dose timepoint during the 26 week treatment period Frequency and titres of binding anti-drug antibodies (ADAs) to GSK3511294, before and after GSK3511294 administration.

* PK parameter abbreviations: AUC(0- ∞) = area under the concentration-time curve from time zero (pre-dose) extrapolated to infinite time; AUC(0-t) = area under the concentration-time curve from time zero (pre-dose) to last time of quantifiable concentration within a participant across all treatments; AUC(0-WeekN) = area under the concentration-time curve from time zero to WeekN; %AUCex = percentage of AUC(0- ∞) obtained by extrapolation; Cmax = maximum observed concentration; tmax=time of occurrence of Cmax; tlast = time of last quantifiable concentration; CL/F = apparent clearance following subcutaneous dosing; Vz/F = apparent volume of distribution after subcutaneous administration; λ_z = terminal elimination rate constant; t $\frac{1}{2}$ = terminal phase half-life.

Primary Pharmacokinetic Estimand:

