6.2.4. Assessment Window

- Scheduled and unscheduled assessments will be considered for summary tables that display data by visit.
- All scheduled and unscheduled data will be considered for each assessment window.
- In summary tables, only scheduled timepoints for that cohort and assessment will be displayed. For example, complement data are not expected to be collected at all timepoints; if any complement data were taken e.g. at Week 2 then they will not be summarised.
- Only 1 value per participant, assessment and assessment window will be used in the calculation of summary statistics for that assessment; if a participant has more than 1 valid observation within an assessment window then the observation closest to the planned time will be used. If 2 observations are equidistant from the planned timepoint then the mean of the values will be taken.
-

Analysis Set / Domain	Parameter (if applicable)	Target	Analysis Window		Analysis Timepoint
			Beginning Timepoint	Ending Timepoint	
Safety and Complement (C3 & C4) data presented by visit.	ECG, vital signs, laboratory (clinical chemistry, urinalysis and haematology), complement (C3 & C4)	Day -1	Any time on Day -1. Note that if there is no scheduled Predose-assessment for the parameter then latest valid result prior to Day 1 dosing should be used		Day -1
	Immunogenicity, ECG, vital signs	Day 1 (Predose)	≤ 2h prior to dosing time		Day 1 (Predose)
	ECG, vital signs	Day 1 (2h)	Day 1 (1.25h)	Day 1 (2.75h)	Day 1 (2h)
	ECG, vital signs	Day 1 (8h)	Day 1 (7.25h)	Day 1 (8.75h)	Day 1 (8h)
	ECG, vital signs, haematology	Day 2 (24h)	Day 2 (23h)	Day 2 (25h)	Day 2 (24h)
	ECG, vital signs, haematology	Day 3 (48h)	Day 3 (47h)	Day 3 (49h)	Day 3 (48h)
	ECG, vital signs, haematology	Day 5	Assessment must have been done on Day 5		Day 5
	ECG, vital signs, laboratory (clinical chemistry, urinalysis and haematology), complement (C3 & C4)	Day 8 (Week 1)	± 1 day		Day 8 (Week 1)
	ECG, vital signs, haematology	Day 15 (Week 2)	± 1 day		Day 15 (Week 2)
	Immunogenicity, ECG, vital signs, laboratory (clinical chemistry, urinalysis and haematology), complement (C3 & C4)	Day 29 (Week 4)	± 3 day		Day 29 (Week 4)
	ECG, vital signs, laboratory (clinical chemistry, urinalysis and haematology), complement (C3 & C4)	Day 57 (Week 8)	± 3 day		Day 57 (Week 8)
	Immunogenicity, ECG, vital signs, laboratory (clinical chemistry, urinalysis and haematology), complement (C3 & C4)	Day 85 (Week 12)	± 3 day		Day 85 (Week 12)

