6.2.5. Multiple measurements at One Analysis Time Point

Mean of the measurements (e.g., ECG) will be calculated and used in any derivation of summary statistics but if listed, all data will be presented.

If there are two values within a time window the value closest to the target day for that window will be used. If values are the same distance from the target, then the mean will be taken.

Participants having both High and Low values for Normal Ranges at any post-baseline visit (including post-baseline unscheduled assessments) for safety parameters will be counted in both the High and Low categories of “Any visit post-baseline” row of related summary tables. This will also be applicable to relevant Potential Clinical Importance summary tables.

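### SAP 6.2.4 and 6.2.5 let a repeat ordered because a laboratory value was clinically significantly abnormal displace that value in by-visit summaries

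*Protocol*

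**What the plan says.** **Trigger (Protocol 8.2.4).** "All laboratory tests with values considered clinically significantly abnormal during participation in the study should be repeated". The same sentence sets the end point: such tests "should be repeated until the values return to normal or baseline or are no longer considered significantly abnormal". For liver events, Protocol Appendix 5 asks for repeat chemistries within 24 hours or within 24 to 72 hours, depending on bilirubin and INR.

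**Choice of value (SAP 6.2.4).** "Scheduled and unscheduled assessments will be considered for summary tables that display data by visit". One value per participant and window is kept: "if a participant has more than 1 valid observation within an assessment window then the observation closest to the planned time will be used". For ties, "If 2 observations are equidistant from the planned timepoint then the mean of the values will be taken". SAP 6.2.5 restates the rule in terms of the target day: "If values are the same distance from the target, then the mean will be taken". Neither section gives the scheduled value precedence or sets aside repeats prompted by the result.

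**Windows (SAP 6.2.4).** Chemistry, urinalysis and C3/C4 have six post-dose visits: Day 8 (±1 day) and Days 29, 57, 85, 169 and 183 (±3 days). Haematology also has ±1 hour windows at 24 h and 48 h, a same-day window at Day 5, ±1 day at Day 15 and ±3 days at Day 127.

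**What is summarised.** SAP 1.1 names as a secondary endpoint "Change from baseline in laboratory safety data, at each post-dose timepoint during the 26 week treatment period", and separately C3/C4 values and their ratio to baseline. SAP 4.3.2 plans laboratory shift categories by visit and worst-case post-baseline. SAP 4.3.3 plans C3/C4 summaries by visit only.

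**The concern.** Which value represents a participant at a visit should not depend on what that value was. Here it can. A value that worries nobody is not repeated, so the scheduled draw stands. A value judged clinically significant is repeated, often within days, and the repeat then competes with it for the same window. If the abnormality is settling, the rule acts mainly on the extreme values and pulls them back.

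Each dose level has 10 participants, so one person's excursion carries a tenth of the visit mean. C3 and C4 deserve particular attention. Protocol 7.5 lists a fall in complement among the findings that may suggest vasculitis, yet SAP 4.3.3 specifies no worst-case output for them and SAP 6.2.1.1 gives them no potential-clinical-importance limit.

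**Working it through.** The plan gives no figure for this point, so there is none to reproduce.

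**1. When a repeat displaces the scheduled value.** Let *s* be the day of the scheduled draw relative to target and *k* the days to the repeat, which then falls at *s* + *k*. If both lie in the window:

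- replaced if |*s* + *k*| < |*s*|, that is, *s* < 0 and 0 < *k* < 2|*s*|;
- averaged if |*s* + *k*| = |*s*|, that is, *k* = 2|*s*|, or *k* = 0 if distance is counted in days;
- otherwise kept. For *s* ≥ 0 and *k* ≥ 1 the scheduled value is always kept.

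**2. How often, given a repeat.** The documents give neither actual visit offsets nor repeat delays. Assumptions: laboratory visits follow the PK sampling windows in the Schedule of Activities (footnote h), *k* is 1, 2 or 3 days, and all combinations have equal weight.

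| Visits | Offset *s* | Combinations | Replaced | Averaged | Kept |
|---|---|---|---|---|---|
| Days 8, 15, 29, 57 | ±1 | 3 × 3 = 9 | 1 | 1 | 7 |
| Days 85, 127, 169 | ±2 | 5 × 3 = 15 | 4 | 1 | 10 |
| Day 183 | ±3 | 7 × 3 = 21 | 7 | 1 | 13 |

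So the value is replaced or averaged in 2/9 (22%), 5/15 (33%) and 8/21 (38%).

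**3. Effect on a cohort mean when it happens.** With *n* = 10, replacement changes the mean by (repeat − scheduled)/10 and averaging by half of that. Illustration with assumed values: ALT ULN 40 U/L, baseline 20, nine participants unchanged, scheduled Day 28 value 130 (3.25 × ULN), Day 29 repeat 78 (1.95 × ULN).

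- Scheduled value: (130 − 20)/10 = +11.0 U/L.
- Replaced under the SAP rule: (78 − 20)/10 = +5.8 U/L, which is 47% lower.
- Same-day repeat of 78, averaged: (130 + 78)/2 = 104, and (104 − 20)/10 = +8.4 U/L, which is 24% lower.

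Averaged over the combinations in step 2, with the same two values throughout, the loss is (1 × 5.2 + 1 × 2.6)/9 = 0.87 U/L at Days 8 to 57, (4 × 5.2 + 2.6)/15 = 1.56 at Days 85 to 169, and (7 × 5.2 + 2.6)/21 = 1.86 at Day 183. Against 11.0 that is 8%, 14% and 17%.

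**4. Simulation.** 200,000 cohorts of 10 with a ±3-day window. Assumed: each participant has a 10% chance of a 5 SD rise, and repeats are triggered above 3 SD. The true mean shift is 0.50 SD.

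| Draws and repeats | Rise gone at repeat | Rise half gone |
|---|---|---|
| All on target, repeat 1–3 days later | 0.50 | 0.50 |
| Draws within ±1 day, repeat 1–3 days later | 0.42 | 0.46 |
| Draws within ±3 days, repeat 1–3 days later | 0.32 | 0.41 |
| Every repeat on the same day, averaged | 0.25 | 0.37 |

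The attenuation runs from none to half, depending on inputs that the documents do not give.

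**The case against.** **The signal is not lost.** This stands. The worst-case laboratory rows in SAP 4.3.2 use every on-treatment value, scheduled or not. SAP 6.2.5 includes unscheduled values in any-visit post-baseline rows and extends this to potential-clinical-importance tables. Listings show all data, and Protocol 8.2.4 has clinically significant changes recorded as AEs. A reader might infer from the ALT example that the 130 U/L value escapes the 2 × ULN flag; it does not. The protection has limits, though: the worst-case laboratory shift table is categorical and says nothing about size, and SAP 4.3.3 offers no equivalent for C3/C4.

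**Shift tables.** A reader might infer that by-visit shift categories are generally corrupted. In the example 130, 104 and 78 are all above the ULN of 40, so the participant stays in the *To High* category. The category changes only if the value used is back in range.

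**ECG.** A reader might extend the point to QTcF, since Protocol 7.4.2 also orders triggered repeats: "Direct observation for 24 hours before discharge with 48 h ambulatory Holter monitor and subsequent repeat assessment at 48 h". The documents support this only weakly. SAP 4.3.5 takes the worst finding when several ECGs share a planned timepoint, reports parameter shifts as worst-case post-baseline, and bases QTcF categories on the maximum. Only the by-visit mean ECG changes share the exposure.

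**Direction and reach.** The bias is towards no change only while the value is resolving. A value still worsening would be displaced the other way, and a symptom-prompted sample under Protocol 7.5 could displace a normal scheduled value. Across all assessments only 6 of 13 post-dose targets have ±3-day windows, although for chemistry and C3/C4 it is 5 of 6. Next-day repeats cannot enter the hour-based or Day 5 windows. Both objections stand and narrow the point.

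**Further conventions are left to the Output and Programming Specification.** That document is not available here. It does not settle the matter, because the SAP states an explicit rule and a different one there would contradict it.

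**Conclusion.** The point holds for by-visit mean laboratory changes, by-visit C3/C4 values and ratios and, where the value used is back in range, by-visit laboratory shift categories. The stated rule makes these summaries depend on the outcome and, for resolving abnormalities, moves them towards no change.

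The size is conditional. Given a triggered repeat, replacement or averaging occurs in 22% to 38% of combinations under the assumed visit windows and delays; the 38% belongs to Day 183 alone. A same-day repeat is averaged if distance is counted in days, as the reference to the target day in SAP 6.2.5 suggests. How often clinically significant abnormalities will occur is not stated.

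The documents do not support a reading that safety conclusions or the decision to open the 300 mg cohort are compromised. The study has no formal tests, the delay criteria in Protocol 5.5 rest on AEs, SAEs and biopsy findings, and the abnormal value survives elsewhere in the report. This should be corrected because the repair is simple, but it does not threaten the study.

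**What to change.** Amend SAP 6.2.4 and 6.2.5:

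- For by-visit summaries and by-visit shift categories, use the scheduled assessment whenever it is present and technically valid. Use an unscheduled or repeat value only when it is not, and then apply the closest-to-target rule.
- Limit averaging to planned replicates: triplicate ECGs, and triplicate pre-dose blood pressure and heart rate.
- Keep every repeat in the worst-case, maximum QTcF and potential-clinical-importance outputs and in the listings.

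With scheduled-value precedence, the attenuation from repeats is zero wherever a valid scheduled value exists; in the ALT illustration the Week 4 mean change stays at +11.0 U/L. The cost is about two sentences in the SAP and a change of sort order in programming, with no new data. Protocol 8.2.4 needs no change for this purpose.
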